**Telemedicine Team Clinical Decision-Making Algorithm**

\*Teledermatologist will be given Nevisense data to assess impact of Nevisense score on decision to biopsy, however, if imaging concerning for malignancy, biopsy will always be recommended given that this device is being used in an investigational setting.

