### **2.3 Rationale**

Detection of melanoma at its earliest stages is associated with high surgical cure rates, without the need for additional, potentially toxic and expensive systemic therapies. Rural and other medically underserved communities have higher rates of melanoma mortality that is associated with reduced access to dermatologic diagnostic services. We aim to study the effectiveness of an augmented telemedicine diagnostic platform for melanoma and other skin cancers that can potentially be deployed in pharmacies and urgent care centers that would be more available in rural communities than dermatologist offices.

The study will evaluate participant-selected lesions of adults in the New York City metropolitan area to simulate the walk-in clinic or pharmacy community setting. The control is an in-person evaluation by a community dermatologist, the current gold

standard. We aim to assess the sensitivity and specificity of the platform compared to the in-person dermatological examination in the diagnosis of melanoma and other skin cancers. Since the Nevisense evaluation is one component of the platform, and the current FDA approval is for it to be used in dermatologist offices to aid in biopsy decisions, we will also examine the degree to which teledermatologists can use the clinical and dermoscopy images to evaluate whether each study lesion would have been appropriate for the Nevisense evaluation had they seen the patient in-person. Finally, we will examine whether the combined teledermoscopy/clinical images plus Nevisense will have greater sensitivity and specificity to diagnose melanoma and other skin cancers than either approach alone.

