### **3.2 Secondary Objectives**

1. To compare the diagnostic accuracy of the enhanced telemedicine method, and its separate individual components (Nevisense, teledermoscopy), to the in-person dermatologist with respect to the diagnosis of skin cancer (confirmed histopathologically).

- i. At the conclusion of the study, and as an additional control, the in-person dermatologist will review the enhanced telemedicine data to compare her in-person diagnoses with diagnoses she would have provided had she been functioning as the teledermatologist.
2. To assess patient satisfaction and preferences (patient-centered outcomes) regarding the teledermatologist evaluation for skin lesions suspicious for skin cancer
3. To determine the proportion of participant-selected skin lesions for which the Nevisense measurement would be considered appropriate by the in-person and teledermatologists.
4. To create a database of dermoscopic images and Nevisense scores of the benign and malignant skin lesions encountered in the walk-in clinic setting.

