#### 4.2.2 Secondary Study Endpoints

Secondary endpoints include:

1. The performance metrics of the telemedicine system in diagnosing skin cancer. We will calculate the sensitivity, specificity, positive and negative predictive values of the telemedicine system and the in-person dermatologist. We will also separately calculate those metrics for the individual components of the telemedicine system, namely, the teledermoscopy imaging and the Nevisense measurement.
2. The satisfaction of the participants with the telemedicine evaluation. This endpoint, based on questionnaire responses, will contribute to achieving the secondary objective of determining the degree to which the telemedicine system would satisfy patient needs and preferences.
3. The proportion of lesions for which the Nevisense evaluation would be considered appropriate and helpful in arriving at the final biopsy recommendation. This endpoint will help achieve the secondary objective of determining the usefulness of Nevisense in the evaluation of participant-selected lesions concerning for skin cancer.

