### 7.3.2 Enrollment/Baseline

#### Enrollment/Initial Visit (Visit 1, Day 1)

- Participant and lesion eligibility confirmed by study personnel
  - This is the formal study screening prior to official enrollment (i.e. signing informed consent)
- Participant given Key Information Sheet with an overview of the study (Supplement Q)
- Conduct informed consent procedure and obtain signed ICF, if not conducted electronically prior to visit
- Assign subject ID for participant
- Obtain demographic information, medical history, medication history as part of enrollment questionnaire (Supplement K). If not conducted electronically prior to visit
- Acquire clinical images, dermoscopic image, and Nevisense data for each lesion
  - Nevisense procedure: the lesion is cleansed with an alcohol wipe and the electrical impedance measurement is conducted using a spring-loaded probe and disposable electrode measuring 5mm x 5mm. The measurement takes <1 minute and the electrical impedance score (EIS) will be recorded. Larger lesions may require a second measurement at another location within the lesion.
  - Record any adverse events from the procedure
  - Neither participants nor the in-person dermatologist will be aware of the score.
- Study team will number the skin lesions using Devon Skin Marker to verify same lesion evaluated across all assessments including the in person dermatologist
- Fill out questionnaire assessing telemedicine evaluation experience so far (Supplement L)
- In-person dermatologist examination of lesion(s) using naked eye and dermoscopy
- If a biopsy is recommended by the in-person dermatologist, participant will be offered a skin biopsy procedure or offered a second appointment within 1-2 weeks for the biopsy procedure
  - If a biopsy is performed, the participant is given at-home instructions for wound care (Supplement R) and the expected wait time for the biopsy results
  - Alternatively, the participant can choose to have the procedure done at another facility. The signed ICF includes permission for the study team to obtain those medical records
  - Follow-up care to the skin biopsy will proceed per standard clinical practice and includes result communication, wound care monitoring, suture removal if applicable and recommendations for follow-up care.
- If a biopsy is not recommended by the in-person dermatologist, the participant is given the expected wait time for telemedicine recommendation phone call.

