#### 10.3.3 Analysis of the Secondary Endpoint(s)

Secondary endpoint (1) will be a descriptive analysis of Sensitivity, Specificity, Positive Predictive Value, and Negative Predictive Value, using the histopathology results as the gold standard. We will assess potential difference or advantages in terms of: a) enhanced telemedicine diagnostic system; b) telemedicine Nevisense alone; c) telemedicine clinical + dermoscopy alone; and d) in-person dermatologist diagnosis. Sensitivity, Specificity, Positive Predictive Value, and Negative Predictive Value will be reported with an upper and lower confidence interval. Lesions with missing data will not be included in the relevant analyses (see Study Design schematic footnote 3). Participants lost to follow-up for reporting his/her biopsy results will be included in the analysis as the data required for analysis has been collected.

As another secondary endpoint, we will be evaluating the enhanced telemedicine service's impact on patient centered outcomes. Descriptive statistics for this secondary endpoint (2) (patient questionnaires, Supplement L will be presented as percentages. Study completion questionnaires may be qualitatively analyzed for themes and quantified by thematic representation across participants. Participant agreement of thematic categories will be calculated as percentages as a summary measure. Factors for stratification may include participants with a biopsy procedure and those without biopsy procedure as well as diagnosis of malignancy or benign lesion within those with biopsy. Participants with missing study completion questionnaire results due to inadequate duration of phone call will not be included.

As a final secondary endpoint (3), we will estimate the number of lesions that may benefit from the additional information of the Nevisense score to the clinical and dermoscopic exam. This estimation will be provided by the in-person dermatologist, and separately by each of the three teledermatologists (Supplement T & U). The estimates will be expressed as percentages. Any lesion with missing data in the in-person dermatologist and teledermatologist plan will not be included in analysis. Participants lost to follow-up will still be included in analysis of this endpoint as required data for this endpoint determination has been captured in the first visit.

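### Secondary endpoint 3 is reported as one percentage per assessor, which cannot show whether remote and in-person dermatologists judge the same lesions suitable for Nevisense

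*Combined protocol and SAP*

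**What the plan says.** Section 2.3 sets an aim at the level of the lesion. The study is to examine "the degree to which teledermatologists can use the clinical and dermoscopy images to evaluate whether each study lesion would have been appropriate" for Nevisense, supposing the reader had seen the patient in person.

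Three later sections describe the corresponding quantity in different words:

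- Section 3.2, objective 3: "To determine the proportion of participant-selected skin lesions for which the Nevisense measurement would be considered appropriate by the in-person and teledermatologists".
- Section 4.2.2, endpoint 3: "The proportion of lesions for which the Nevisense evaluation would be considered appropriate and helpful in arriving at the final biopsy recommendation".
- Section 10.3.3, analysis: "we will estimate the number of lesions that may benefit from the additional information of the Nevisense score to the clinical and dermoscopic exam". On who rates: "This estimation will be provided by the in-person dermatologist, and separately by each of the three teledermatologists". On the summary: "The estimates will be expressed as percentages".

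No cross-tabulation, agreement measure or confidence interval is given for endpoint 3. Kappa with confidence intervals appears in section 10.3.2, but for the biopsy recommendation.

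On access to the score, section 7.3.2 says of Visit 1: "Neither participants nor the in-person dermatologist will be aware of the score". Section 4.1 also places this masking at the time of the visit. The note to the telemedicine decision algorithm says: "Teledermatologist will be given Nevisense data to assess impact of Nevisense score on decision to biopsy". The same note adds that a lesion whose imaging raises concern for malignancy is always recommended for biopsy.

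**The concern.** Whether remote readers judge suitability as it would be judged in person is a paired question: for each lesion, do the two judgements match? One percentage per assessor discards the pairing. Two assessors can report the same percentage while choosing different lesions, so close percentages could be read as good remote judgement when agreement is no better than chance.

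The shift in wording adds a second, smaller problem. *Appropriate* and *may benefit* are forward judgements that need no score. *Helpful in arriving at the recommendation* can be read as a statement about what the score did. An assessor who has not seen the score can give the first kind of answer but not the second. Unless the sections are aligned, a reader of the results will not know which quantity the four percentages represent.

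**Working it through.** **Inputs.** Four assessors (10.3.3). About 500 participants with 2 lesions each on average (10.4). The documents give no expected percentage appropriate, kappa or within-participant correlation, so those below are assumptions.

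**The plan's own figures.** 500 × 2 = 1000 lesions. At 10%, 500 to 1000 lesions give 50 to 100 biopsy recommendations and 450 to 900 lesions without one. These match section 10.4. No figure is stated for endpoint 3.

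**What two percentages allow.** Let the assessors rate proportions p and q appropriate, and let a be the proportion that both rate appropriate.

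- Limits on a: max(0, p + q - 1) ≤ a ≤ min(p, q)
- Raw agreement: Po = 1 - p - q + 2a
- Chance agreement: Pe = pq + (1 - p)(1 - q)
- Kappa = (Po - Pe)/(1 - Pe)

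With p = q = 0.30, Pe = 0.09 + 0.49 = 0.58:

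- No overlap (a = 0): Po = 1 - 0.60 = 0.40; kappa = (0.40 - 0.58)/0.42 = -0.43.
- Chance overlap (a = 0.09): Po = 0.58; kappa = 0.
- Full overlap (a = 0.30): Po = 1; kappa = 1.

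Per 1000 lesions, each assessor reports 300 in all three cases, yet they disagree on 600, 420 or 0 lesions.

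| Percent appropriate (two assessors) | Raw agreement | Kappa |
|---|---|---|
| 10 and 10 | 80% to 100% | -0.11 to 1 |
| 20 and 20 | 60% to 100% | -0.25 to 1 |
| 30 and 30 | 40% to 100% | -0.43 to 1 |
| 50 and 50 | 0% to 100% | -1 to 1 |
| 30 and 40 | 30% to 90% | -0.52 to 0.78 |

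**Precision if agreement is added.** The large-sample (Fleiss-Cohen-Everitt) variance of kappa is (A + B - C)/[n(1 - Pe)²]. For p = q = 0.30 and an assumed kappa of 0.6:

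- Po = 0.58 + 0.6 × 0.42 = 0.832. The cells are 0.216 (both yes), 0.616 (both no) and 0.084 for each type of disagreement.
- A = 0.216(1 - 0.6 × 0.4)² + 0.616(1 - 1.4 × 0.4)² = 0.2440
- B = 0.4² × 2 × 0.084 = 0.0269
- C = (0.6 - 0.58 × 0.4)² = 0.1354
- With n = 1000: SE = √(0.1355/1000)/0.42 = 0.0277, so the 95% half-width is 1.96 × 0.0277 = 0.054.

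| Half-width for kappa = 0.6 | 10% appropriate | 30% | 50% |
|---|---|---|---|
| 1000 lesions, no clustering | 0.08 | 0.05 | 0.05 |
| 1000 lesions, design effect 1.5 (assumed) | 0.10 | 0.07 | 0.06 |
| 500 lesions, no clustering | 0.12 | 0.08 | 0.07 |

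The ratings the plan already collects would therefore estimate agreement usefully.

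**Who can rate what.** Section 10.3.3 says the data for this endpoint are captured at the first visit, when the in-person dermatologist is masked (4.1, 7.3.2). That rating can express whether the score might help, not whether it did. The teledermatologists receive the score. Method (c) in 10.3.3 needs a result from clinical and dermoscopic images alone, so a comparison without and with the score is within reach.

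**The case against.** The best defence is that the objective and endpoint are proportions, and proportions are what the plan reports. Section 2.3 describes the remote reader's own counterfactual judgement and does not name the in-person dermatologist as reference. The remote readers are pigmented-lesion experts (6.1.4) and the comparator is described as a community dermatologist (2.3), so disagreement would mix reader differences with modality differences. The study tests no hypothesis (10.1), and a cross-tabulation could be added at analysis.

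Much of this stands. The percentages do satisfy objective 3, and the mixing of reader and modality must be stated beside any agreement result. But the in-person rating is the in-person comparator the plan collects for this judgement, and without pairing the section 2.3 aim gets no lesion-level answer.

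A reader might infer more than the documents support:

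- *That the in-person dermatologist never sees the score.* Section 4.1 limits masking to the visit, and section 3.2 plans an end-of-study review of the telemedicine data, though for diagnoses.
- *That masking invalidates the in-person rating.* A masked dermatologist can properly judge in advance whether a lesion may benefit.
- *That the teledermatologists' ratings are contaminated by the score.* The order of rating may be fixed in Supplement U or the algorithm figure, neither of which was available. Section 2.3 speaks of judging from images.
- *That remote readers choose lesions for Nevisense here.* Measurement takes place at Visit 1, mostly by non-physician staff (6.2, 7.3.2), before the remote read.
- *That usefulness rests on opinion alone.* Sections 10.3.2 and 10.3.3 already compare the combined method with its components.

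**Conclusion.** The concern holds in a limited form. Endpoint 3 as analysed answers objective 3 but cannot show lesion-level agreement, which bears directly on the section 2.3 aim. At an illustrative 30% each, the same pair of percentages fits agreement from 40% to 100%. The limits at either end are extremes, not forecasts; the point is that the planned summary cannot distinguish them. This holds for any pair of percentages strictly between 0 and 100.

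The wording of the endpoint also needs aligning, because the in-person rating supports only the prospective meaning. Whether the teledermatologists rate before seeing the score is an open question for the sponsor, not a demonstrated flaw. The matter is modest: a descriptive secondary endpoint in a pilot, with the paired ratings already planned.

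**What to change.** 1. In section 10.3.3, keep the percentages and add, for each teledermatologist, the lesion-level cross-tabulation against the in-person rating. Report raw agreement, positive agreement 2a/(p + q), negative agreement 2d/(2 - p - q), where d is the proportion both rate not appropriate, and kappa. Use confidence intervals that allow for several lesions per participant. Give each reader's denominator, since section 10.5 allows two readers when one is absent. State that disagreement mixes reader and modality differences.
2. Use one definition in sections 3.2, 4.2.2 and 10.3.3: a prospective judgement that Nevisense is appropriate or may benefit the evaluation, made by all four assessors.
3. If a result on helpfulness is wanted, take it from the teledermatologists only, as the proportion of lesions whose biopsy recommendation differs between the images-only read (method c) and the read with the score. Under the algorithm's rule for concerning images, such changes will run largely from no biopsy to biopsy, and the report should say so.
4. Confirm from Supplement U that appropriateness is rated before the score is shown.

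The cost is minor SAP wording and a small amount of analysis, with no extra reader, visit or procedure.

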**10.3.4 Safety Analyses**

Safety events will be coded in a medical dictionary for similar presentations of symptoms, signs, illness, or experience. Each AE will be counted once for a given participant and will be presented with severity, frequency, and relationship to the diagnostic method. The outcome and duration of each AE will also be presented. AE will be ascertained as those that are reported to the study team at the relevant visit. All AEs leading to premature termination or withdrawal from study and all SAEs will be presented in a table.

**10.3.5 Adherence and Retention Analyses**

Adherence is not applicable. Participation is defined as all subjects that enroll into the study. Study retention is defined as participants that complete all visits through the last visit (study completion questionnaire) out of the number of subjects enrolled. Participants lost to follow up include all those that were unable to be contacted for biopsy scheduling, wound check, or study completion questionnaire administration.

**10.3.6 Baseline Descriptive Statistics**

Baseline characteristics used for baseline descriptive statistics include demographic information, past medical history of skin cancer, family history of skin cancer, natural hair color, eye color, tanning bed exposure, moderate to severe sunburn exposure, history of atypical or dysplastic nevi, estimate of number of moles on body, and estimate of number of freckles on face. Inferential statistics will not be used.

**10.3.7 Planned Interim Analysis**

Not applicable

**10.3.7.1 Safety Review**

Not applicable

**10.3.7.2 Efficacy Review**

Not applicable

**10.3.8 Additional Sub-Group Analyses**

Primary endpoint and secondary endpoints will be analyzed by age, sex, and race/ethnicity.

**10.3.9 Multiple Comparison/Multiplicity**

Not applicable

**10.3.10 Tabulation of Individual Response Data**

Not applicable

**10.3.11 Exploratory Analyses**

Exploratory analysis may be conducted using the continuous Nevisense score or categorical unequivocally benign lesion designation (using clinical and dermoscopic image alone) as factors of stratification before re-evaluation of primary endpoint again.

**10.4 Sample Size**

Number of subjects to recruit and screen is estimated to be 650 or fewer. Number of participants eligible is estimated to be 500 or fewer. Based on the previously mentioned Norwegian study, we anticipate a biopsy recommendation rate of 10% between the telemedicine and in-person evaluations. With each participant presenting with 1-3 lesions, an estimate of 1000 evaluated lesions (2 per participant on average) is possible. Assuming a biopsy recommendation 10% from this historical data, there will be likely 50 - 100 biopsies recommended and 450 - 900 lesions not recommended for biopsy.

We anticipate 2% of the sample will be lost to follow up based on historical data. Missing data is estimated at 4% based on those lost to follow up and technical error based on historical data. We anticipate 1% of participants to withdraw based on historical data. Participants who have formally withdrawn from the study will not be included in primary or secondary endpoint analysis, nor will they be included in the analysis datasets.

## **10.5 Measures to Minimize Bias**

### **10.5.1 Enrollment/Randomization/Masking Procedures**

**10.5.2** Subjects will be self-enrolled into the study by viewing an advertisement and making an appointment for enrollment at the DCSU. Enrollment procedures include eligibility verification and informed consent confirmation with signature. The in-person dermatologist (control arm) and telemedicine team (intervention arm) will each be blinded to the other's management recommendation. The in-person dermatologist will be blinded to the Nevisense score. Additionally, the teledermatologist team of 3 physicians will be masked to each other's management plan. If one teledermatologist is absent (due to vacation, illness etc.) and cannot make their recommendations, a minimum of 2 teledermatologists is satisfactory to make a consensus. If any teledermatologist recommends biopsy, the team recommendation will be biopsy. Periodic reviews of teledermatology diagnoses by the teledermatology team will be held in order to improve quality control during the study. **Evaluation of Success of Blinding**

Not applicable

### **10.5.3 Breaking the Study Blind/Participant Code**

Breaking the study blind for all participants may occur in the event of an SAE. Both intentional and unintentional breaking of the blind will be reported to the principal investigator.

## **11 Source Documents and Access to Source Data/Documents**

Source data is all information, original records of clinical findings, observations, or other activities in a clinical trial necessary for the reconstruction and evaluation of the trial. Source data are contained in source documents. For this study source documents will include case record forms (CRFs), clinical and dermoscopic images, patient questionnaires, in-person and teledermatologist data collection forms, and pathology reports. All data collected using paper documentation will be transferred to an electronic CRF maintained in REDCap. Paper copies for auditing purposes will be kept in a locked file cabinet in a locked office in the Dermatology Department. Images will be maintained on a NYULH computer server in a Department of Dermatology dedicated folder or in Epic.

The study case report form (CRF) is the primary data collection instrument for the study. All data requested on the CRF must be recorded. All missing data must be explained. If a space on the CRF is left blank because the procedure was not done or the question was not asked, write "N/D". If the item is not applicable to the individual case, write "N/A". All entries should be printed legibly in black ink. If any entry error has been made, to correct such an error, draw a single straight line through the incorrect entry and enter the correct data above it. All such changes must be initialed and dated. **DO NOT ERASE OR WHITE OUT ERRORS.** For clarification of illegible or uncertain entries, print the clarification above the item, then initial and date it.

